2.3 Subject Disposition, Demographics and Other Baseline Characteristics

Unless noted otherwise, summaries and listings described in this section will be based on the FAS.

2.3.1 Subject disposition

The following will be tabulated:

- Number (%) of patients treated;
- Number (%) of patients who are still on-treatment at the time of cut-off;
- Number (%) of patients who discontinued treatment and primary reasons for discontinuation.

A listing of disposition will be produced.

2.3.2 Demographics

All demographic and baseline disease characteristics data will be summarized and listed. Categorical data, eg, gender, age groups: <65 years vs ≥65 years, race, ECOG performance status, will be summarized by frequency counts and percentages; the number and percentage of patients with missing data will be provided. Continuous data, eg, age, weight, height will be summarized by descriptive statistics (N, mean, median, standard deviation, Q1, Q3, minimum and maximum).

2.3.3 Medical History

Summary of medical history will be provided by SOC and PT, using the Medical Dictionary for Regulatory Activities (MedDRA) (version 21.0 or later) terminology available at the time of reporting.

2.3.4 Prior Antineoplastic Therapy

The number (%) of patients who received any prior anti-neoplastic medication, radiotherapy or surgery will be summarized. The summary will include only the prior antineoplastic therapy after or on the date of the initial diagnosis of cholangiocarcinoma.

The summary of prior anti-neoplastic medications will include the total number of regimens (note: there can be more than one medication per regimen) and the total number of lines (excluding adjuvant or neoadjuvant regimens), setting at last treatment, best response at last treatment (defined to be the best response during the last treatment regimens recorded), best response during treatment with gemcitabine and cisplatin. For this analysis, gemcitabine and gemcitabine hydrochloride will be grouped to define prior treatment with gemcitabine. Prior

antineoplastic medications will also be summarized by Anatomical Therapeutic Chemical (ATC) class, and preferred term. The summary of the efficacy endpoints, including response assessment, duration of response and time to progression, on the 1st line of gemcitabine base therapy will also be provided.

The summary of prior anti-neoplastic radiotherapy will include the total number of subjects who received prior anti-neoplastic radiotherapy, the radiotherapy locations, (including all locations recorded for each patient), setting at last radiotherapy.

The summary of prior anti-neoplastic surgery will include the time (in months) between the last surgery (non-biopsy procedure) to start of study treatment, procedure at last surgery and residual disease at last surgery.

2.3.5 *Diagnosis and Extent of Cancer*

The summary and listing of diagnosis and extent of cancer (disease history) will include primary site of cancer, details of tumor histology/cytology, histologic grade, stage at initial diagnosis, time (in months) since initial diagnosis of primary site to treatment start, time (in months) from initial diagnosis to first recurrence/relapse, time (in months) since most recent recurrence/relapse to treatment start, current extent of disease (metastatic sites).

2.4 Protocol Deviations

Unless otherwise specified, the FAS will be used for the protocol deviation summary tables and listing. The number (%) of patients with any CSR-reportable protocol deviation will be tabulated by the deviation category as listed below:

- Subject enrolled and did not satisfy the entry criteria
- Subject developed study/treatment withdrawal criteria during the study, but was not withdrawn
- Subject received the wrong treatment or incorrect dose
- Subject took a prohibited concomitant medication
- Major procedural or other GCP deviation that potentially affects patient safety or efficacy data interpretation

2.5 Treatments (Study Treatment, Concomitant Therapies, Compliance)

2.5.1 *Study Treatment*

Unless otherwise specified, the full analysis set will be used for all summaries and listings of study treatment.

2.5.1.1 *Data Analysis*

Duration of exposure, actual cumulative dose, relative dose intensity (RDI) will be summarized in the full analysis set. Duration of exposure will be categorized into time intervals; frequency counts and percentages will be presented for the number (%) of subjects in each interval. The number (%) of subjects who have dose reductions or interruptions, and the reasons, will be summarized by treatment.

Subject level listings of all doses administered on treatment along with dose change reasons will be produced.

2.5.1.2 *Duration of Exposure to Study Treatment*

$$\text{Duration of exposure (day)} = (\text{end date of infigratinib}) - (\text{start date of infigratinib}) + 1,$$

End date of infigratinib refers to the end date of last non-zero dose record with the exception for subjects who are still on treatment. For subjects who are still on treatment, the end date of infigratinib refers to the end date of last dose record.

Then,

$$\text{Duration of exposure (month)} = \text{Duration of exposure (day)} / 30.4375.$$

The duration of exposure to study treatment will be determined by the number of months exposed to infigratinib. Duration of exposure will be summarized using descriptive statistics.

Summary of duration of exposure of study drug will include categorical summaries (based on clinically meaningful time intervals) and continuous summaries (ie, mean, standard deviation etc.) using appropriate units of time.

2.5.1.3 *Cumulative Dose*

Cumulative dose of study treatment is defined as the total dose given during the study treatment exposure and will be summarized.

The **planned cumulative dose** for study treatment refers to the total planned dose as per the protocol up to the last date of investigational drug administration. The **actual cumulative dose** refers to the total actual dose administered, over the duration for which the subject is on the study treatment as documented in the Dose Administration eCRF.

2.5.1.4 *Relative Dose Intensity*

Relative dose intensity (RDI) is defined as the ratio of actual cumulative dose to the planned cumulative dose. For example, a subject take study drug from day 1 to day 21 at 125 mg/day; then from day 29 to day 30 at 100mg/day, and end treatment afterward. The cumulative actual dose = $21*125+100*2=2825$ mg; the planned cumulative dose = $21*125+125*2=2875$ mg. The relative dose intensity = $2825/2875=98.3\%$.

RDI will be summarized. Summary of RDI will include categorical summaries based on the following categories: ≤ 0.5 , $>0.5 - \leq 0.75$, $>0.75 - \leq 0.9$, $>0.9 - \leq 1.0$ and >1.0 .

2.5.1.5 *Dose Reductions, Interruptions*

The number of subjects who have dose reductions, or interruptions, and the reasons, will be summarized separately for the study treatment.

Dose reductions will be summarized by the lowest non-zero dose level. Note that planned 1 week off in dosing schedule will not be collected or counted as dose interruption.

The corresponding fields 'Reason for dose change/dose interrupted' and 'Reason for permanent discontinuation' will be used to summarize the reasons.

2.5.2 *Prior, Concomitant and Post Therapies*

Concomitant therapies are defined as any medications (excluding study treatment, prior antineoplastic treatments) and significant non-drug therapies (including physical therapy and blood transfusions) administered in the study and are recorded in the Prior and Concomitant Medications eCRF. These therapies will be coded using the WHO Drug Reference Listing (WHO DRL) dictionary that employs the WHO Anatomical Therapeutic Chemical (WHO ATC) classification system. Only on-treatment (treatment-emergent) concomitant medication (CM) will be summarized. On-treatment (treatment-emergent) concomitant medication refers to the concomitant medication taken on or after the first administration day of study drug and up to last study administration day of study drug +30 days. Some groups of concomitant medication may also be summarized separately, for example, phosphate-binders.

The imputation of a concomitant medication start date and end date will follow the same conventions as for an AE start date if needed for analyses.

The post antineoplastic medication will be listed.

Prior, concomitant and post therapies may be listed as needed.

2.5.3 *Compliance*

Compliance to the study treatment will be summarized in terms of the RDI or percentage of patients who took a predefined percentage of the number of prescribed. The predefined RDI categories are ≤ 0.5 , $>0.5 - \leq 0.75$, $>0.75 - \leq 0.9$, $>0.9 - \leq 1.0$ and >1.0 . The number and proportion of patients falling in each category will be presented. Details are provided in Section [2.5.1](#).

2.6 *Analysis of the primary objective*

2.6.1 *Variable*

For Cohort 1, the primary objective of the study is to assess anti-tumor activity of infigratinib using overall response rate assessed by central imaging review.

Best overall response (BOR) is the best overall response a subject ever achieves during the study prior to any subsequent anti-cancer therapy. Overall response rate (ORR) is defined as the proportion of patients with a best overall response of confirmed Complete Response (CR) or Partial Response (PR), as per RECIST version 1.1, among the corresponding analysis set.

ORR (central imaging assessment) is the primary efficacy endpoint, and its analysis consists of a Clopper-Pearson 95% CI accompanied by a characterization of time to response (TTR) and duration of response (DOR) to allow for a more complete characterization of the beneficial effect Infigratinib may have in the principal analysis population. The Brookmeyer-Crowley method will be used to construct the 95% CI for each of TTR and DOR.

2.6.2 *Statistical Hypothesis, Model, and Method of Analysis*

For Cohort 1, the primary analysis of the primary endpoint (ORR assessed by central imaging review) should occur when all subjects in Cohort 1 have the potential to be followed for at least 10 months after their initial exposure to study treatment. The formal interim analysis for Cohort 1 will be conducted when all patients in the interim efficacy analysis set have been followed for at least 10 months after their initial exposure to the study treatment. Any confirmed PR or CR until the data cut-off date and any subsequent anti-cancer therapy will be considered as a responder for ORR, irrespective of when it occurred.

2.7 *Analysis of Secondary Objective(s)*

This section describes analyses of secondary objectives for Cohort 1. The same endpoints will be analyzed for Cohorts 2 and 3 as exploratory, so the approaches described in this section also apply to Cohort 2 and 3.

2.7.1 *Secondary Efficacy Objectives*

Overall Response Rate Per Investigator

ORR per investigator is among the secondary endpoints. The estimated ORR will be presented with the corresponding 95% confidence interval based on exact binomial distribution using the corresponding analysis set.

Overall Survival

Overall Survival (OS) is defined as the time from the date of start of treatment to the date of death due to any cause. The survival time for subjects without documentation of death prior to the data cutoff will be censored at the last date the subject was known to be alive prior to the cutoff date. Survival time for subjects with no post-baseline survival information will be censored at the date of start of treatment.

OS will be analyzed using the Kaplan-Meier method. Survival rate at 4, 6, 8, 12, 18, 24 months (and every 6 months thereafter as reported in database) with median OS will be estimated along with 95% confidence intervals.

Progression Free Survival

Progression free survival (PFS) is defined as the date of the start of treatment to the date of the event defined as the first documented progression or death due to any cause, whichever is earlier. If subject has not had an event, progression-free-survival is censored at date of last valid tumor assessment or start of study treatment if there is no valid tumor assessment available. For subjects who had an event after two or more missed visits, the subject will be censored at the last adequate tumor assessment. The PFS analyses will be done based on central and local assessments separately. Kaplan-Meier analysis of PFS will be provided.

The primary PFS will be derived based on all the tumor assessments and death including any after a subsequent anti-cancer therapy. A sensitivity analysis will also be conducted on PFS excluding the tumor assessments and death after any subsequent anti-cancer therapies. If the event (the first progressive disease or death) is after a subsequent anti-cancer therapy, the PFS for the sensitivity analysis will be censored at the last valid tumor assessment prior to all subsequent anti-tumor therapies or first dose date if there is no valid tumor assessment prior to all subsequent anti-tumor therapies.

For Cohorts 2 and 3, the percentage of subjects who are progression-free at the second scheduled scan (approximately 16 weeks from treatment initiation) or later will be analyzed using 95% exact binomial confidence interval. Patients who do not have scans to show that they are progression-free at the second scheduled scan or later will be considered as not benefiting from the study treatment. Sensitivity analysis will be done by estimating PFS >16 weeks using K-M estimate.

Best Overall Response and Disease Control Rate

Overall lesion assessments will be listed by subject. BOR will be summarized for the rate of best overall response of progressive disease, stable disease, confirmed partial response (PR), and confirmed complete response (CR) separately; it will also be summarized for the Disease Control Rate which are the proportion of subjects having respectively a best overall response of confirmed PR or CR, or stable disease. The estimates will be presented along with the corresponding 95% exact confidence interval. Best overall response will be provided for investigator assessment and central assessment as specified by cohort (Section 1.2). In addition, the concordance of best overall response based on central assessment and local assessment will be assessed.

Best tumor burden change (maximum tumor burden reduction from baseline or minimum tumor burden increase from baseline if tumor burden has never reduced prior to any anti-cancer therapy) will be presented graphically.

Response Onset and Duration of Response

Response onset will be estimated using Kaplan-Meier product limit method to analyze TTR based on ORR central imaging assessment. The Brookmeyer-Crowley method will be used to construct the 95% CI for TTR. DOR will be further summarized by length of exposure to

infigratinib using the following exposure cut-off lengths: at least 6 months, at least 9 months, at least 12 months.

Response onset and duration of response (DOR) will be summarized for confirmed responders only, based on local and central assessments separately. Response onset is defined as the time from the first study drug administration date to the initial response date. DOR is defined as the time from the initial response to the date of the event defined as the first documented progression or death due to any cause, whichever is earlier. The same event/censoring rule applied to PFS will be applied to DOR.

2.7.2 *Safety Objectives*

The FAS will be used for summaries and listings of safety data except for the second formal interim analysis for Cohort 1 after amendment 3 where the Interim Analysis Set 2 for Cohort 1 will be used. In general, summaries will be provided only for the on-treatment safety assessments, which are the assessments occurring or taken during the on-treatment period.

2.7.2.1 *Adverse Events (AEs)*

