## 7 VISIT SCHEDULE AND ASSESSMENTS

# 7.1 Study flow and visit schedule

Table 7 lists all of the assessments and indicates with an "X" the visits when they are performed. All data obtained from these assessments must be supported in the patient's source documentation. The table indicates which assessments produce data to be entered into the database (D) or remain in source documents only (S) ("Category" column).

Molecular pre-screening assessments can be done any time prior to the initiation of the screening.

- Baseline imaging assessments can be conducted within 28 days prior to 1st day of study treatment.
- All other baseline/screening assessments must be performed within 21 days prior to 1st treatment, except for the ophthalmic examination, which should be completed within 14 days prior to first treatment.
- Baseline/screening assessments that are conducted within 3 days prior to 1st treatment can be used to satisfy the day 1 requirement. Every effort must be made to follow the schedule outlined in Table 7.

For all visits, there is a  $\pm$  3-day window on assessments to take into account scheduling over weekends and holidays, **if not explicitly specified otherwise**. For post baseline imaging and ophthalmic assessments, a  $\pm$ 7 day window is allowed, except for the first post baseline assessment (+7 day window permitted). There are no visit windows for the trough PK sampling days (sparse PK sample group [Table 10]: Cycle 1 Days 2, 8, 15, and 21; and extensive PK sample group [Table 11]: Cycle 1 Days 2 and 16).

PK samples will be collected according to Table 10 or Table 11. Biomarker sampling will be conducted as outlined in Table 12.

All assessments should be performed as outlined in Table 7 and as clinically indicated.

Table 7: Visit evaluation schedule for all cohorts

Study Period	Category	Protocol Section	Molecular Pre-	Screening a	Cycle 1							Cycle 2 Cycle 3				cycles	End of study treatment EOT	30-day follow-up	Disease Progression follow-up every 8 weeks Follow-u	months after EOT)
Day of Cycle				-21 to	1	2	8	15	16	21	1	15	1	15	1	15	≤14 days of the decision to discontinue the treatment			
Informed consent for molecular pre-screening if local data are not available	D	7.1.1	X																	
Pre-screening testing if local data are not available		7.1.1	X																	
Study Informed Consent (ICF)		7.1.2		X																
Demography	D	7.1.2.3	X	X																

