Inclusion/exclusion criteria	D	5.2, 5.3, 7.1.2	X	X																
Relevant medical history/current medical conditions	D	7.1.2.3		X																
Diagnosis and extent of cancer	D	7.1.2.3		X																
Prior antineoplastic therapy	D	7.1.2.3		X																
Prior/concomitant medications	D	6.3		X	Continuous												X	X		
Physical examination	S	7.2.2.1		X	X		X	X		X	X	X	X	X	X		X			
Height	D	7.2.2.3		X																
Weight	D	7.2.2.3		X	X						X		X		X		X			
Vital signs	D	7.2.2.2		X	X		X	X		X	X	X	X	X	X		X			
Performance status	D	7.2.2.4		X	X						X		X		X		X			
Ophthalmic assessment	D	7.2.2.5		X				X			X		X		Xb		X			
Hematology		7.2.2.6.1		X	X		X	X		X	X	X	X		X		X			
Chemistry (predose)	D	7.2.2.6.2		X	X		X	X		X	X	X	X		X		X			
Coagulation D 7.2.2.6.3			X	If clinically indicated										•						
Urinalysis (microscopic or macroscopic)		7.2.2.6.4		X	If clinically indicated															
Pregnancy test	D	7.2.2.6.5		X	X						X		X		X		X			

	Category	Protocol Section	Molecular Pre- screening	Screeninga	Cycle 1		Cycle 2		Cycle 3		Subsequent		End of study treatment	30-day follow-up	Disease Progression follow-up every 8 weeks	Survival follow- up (every 4 months after EOT)				
Study Period			Screen	ning	Treatment EOT									EOT		Follow-up	 			
Day of Cycle				-21 to -1	1	2	8	15	16	21	1	15	1	15	1	15	≤14 days of the decision to discontinue the treatment			
Tumor response per RECIST 1.1	D	7.2.1		X									X		Day 1 of every odd cycle		X (if not done within 28 days prior)		X (only for pts. who discontinue for any reason other than progression of disease	
Study drug administration	dministration D 6.1 Continuous on a 3 weeks on 1 week off schedule c																			
12-lead ECG	D	7.2.2.7		X	X	X	X	X			X		X		X		X			
Cardiac imaging (ECHO or MUGA)	D	7.2.2.7		X							X						X			
Adverse Events	D	8.1, 8.2						Cor	ntinuo	ously	throu	ghout	the s	tudy				X		
Collection of archival paraffin blocks/slides or a newly obtained tumor sample AND pathology report	D	7.2.4.1	X (if local data not available)	X d																
Newly obtained tumor sample (if medically feasible)		7.2.4.2		Xe	X (upon disease progression)-optional															
Blood sample for assessment of circulating tumor DNA (cell free DNA) (all samples are predose)	D	7.2.4.3		X							X		X		Day 1 of every odd cycle		X (if not done within 28 days prior)			
Blood for PK (sparse PK group)	D	7.2.3.1			X	X	X	X		X	X	X	X	X	,	Day 15 Cycles 4- 6				

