## 7.1.3 Treatment period

The treatment period commences on the first day of the first cycle of BGJ398 and ends after the last dose of BGJ398.

During the study treatment period, patients will be regularly monitored to assess the safety and early anti-tumor activity of treatment. For purpose of scheduling and evaluations, a treatment cycle will consist of 28 days.

During the treatment period, the patient is obliged to follow the investigators instructions with regards to contraception, concomitant medications and dosing regimen. There is no fixed duration; patients may continue treatment with the study drug until the development of an unacceptable toxicity that precludes any further treatment, disease progression, and/or treatment is discontinued at the discretion of the Investigator or by patient refusal. For details of assessments during the treatment period, refer to Table 7.

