1 INTRODUCTION

This Statistical Analysis Plan (SAP) provides detailed statistical methodology for the analysis of data from study CBGJ398X2204 that will be presented in the Clinical Study Report (CSR). The output shells (in-text and post-text) accompanying this document can be found in the Tables, Figures and Listings (TFL) shells document. The specifications for derived variable and datasets can be found in the ADaM Reviewer's Guide. This version of the SAP is based on the Clinical Study Protocol (CSP) CBGJ398X2204 Version 6 (Amendment 5) dated on 15-Jan-2020.

All changes to the planned analysis described in this document required before or after database lock will be made through an amendment or addendum, respectively. Note that obvious corrections will be made at the time of analysis to address minor formatting or spelling mistakes present in the TFL shells document without the need to amend.

The SAP, TFL shells, and ADaM Reviewer's Guide documents may also serve as a reference for the creation of any outputs required outside of the CSR, eg, IB updates, abstracts, posters, presentations, manuscripts, and management updates. Data used for these analyses will have a status aligned to the database lock guidance.

[figure not shown]
The purpose of sections 1.1 to 1.2 is to make the SAP a standalone document and to be more specific on endpoints as required. No clinical background information needs to be included, as this is already provided in the CSP; only information relevant to the analyses is to be included.

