The study day *for safety assessments* (eg, adverse event onset, laboratory abnormality occurrence, vital sign measurement, dose interruption, etc.) that are after the start of study treatment will be calculated as the difference between the date of the event (onset date of an event, assessment date etc.) and the start of study treatment plus 1. The first day of study treatment is therefore study Day 1. Example: if start of study treatment is on 05-Jan-2014 and start date of an adverse event is on 09-Jan-2014 then the study day of the adverse event onset is 5. For safety assessments before start of study treatment, the study day is negative and derived by (date of event – start date of study treatment). For example: if start of study treatment is on 05-Jan-2014 and date of lab measurement is on 02-Jan-2014 then the study day of the laboratory abnormality is -3. Note, the day of start of study treatment is Day 1, and the day before the date of first study treatment is Day -1, not Day 0.

2.1.1.4 *Baseline*

Baseline is the result of an investigation describing the “true” state of the subject before start of study treatment administration.

For safety evaluations, the last available assessment on or before the date of start of study treatment is taken as “baseline” assessment. In case time of assessment and time of treatment start is captured (eg, pre-dose ECG), the last available assessment before the treatment start date/time is used for baseline.

For safety parameters (eg, ECGs or vital signs), where study requires multiple replicates per time point, the average of these measurements would be calculated for baseline (if not already available in the database).

In rare cases where multiple measurements meet the baseline definition, with no further flag or label that can identify the chronological order, then the following rule should be applied: If values are from central and local laboratories, the value from central assessment should be considered as baseline; if multiple values are from the same laboratory (local or central) or collected for ECGs or vital signs, then the average value should be considered as baseline while for the grade of laboratory tests the worst grade will be considered as baseline. For this study, safety laboratory testing is per local site laboratory.

If subjects have no value as defined above, the baseline result will be missing.

2.1.1.5 *On-treatment Assessment/Event and Observation Periods*

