3 SAMPLE SIZE CALCULATION

3.1 Cohort 1

At the time of the first formal interim analysis after amendment 3, the interim efficacy analysis set 1 will include 72 patients with FGFR2 gene fusions or translocations. The half-width of the exact 95% confidence interval for ORR will not exceed 12%.

With at least 106 subjects with FGFR2 gene fusions or translocation will result in the exact 95% confidence interval half-width of ORR less than 10%.

3.2 Cohort 2 and Cohort 3

In Cohorts 2 and 3, patients who are progression-free at the second scheduled post-baseline scan (approximately 16 weeks from treatment initiation) or later will be considered to be benefiting from study treatment. If the lower bound of the patients who are progression-free at the second scheduled post-baseline scan (approximately 16 weeks) or later excludes 20%, the treatment will be considered as benefiting the patients.

For Cohort 2, the percentage of patients who are progression-free at the second scheduled post-baseline scan (approximately 16 weeks) or later will be estimated with 95% exact confidence interval. There will be approximately 20 patients in total. A sample size of 20 will result in the exact 95% confidence interval half width of less than 23%. Patients who withdraw from the study for any reason before the second scheduled scan will be considered as not benefiting from study treatment. Sensitivity analysis will be conducted using the K-M method to estimate PFS >16 weeks.

[Table 8](#) provides some examples of CIs corresponding to observed numbers of patients considered to have benefited from treatment. For example, if 9 of 20 patients are progression-free at the second scheduled post-baseline scan or later, then the lower bound of the 95% exact confidence interval (CI) will exclude 20%.

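### Read at 16 weeks, the Kaplan-Meier sensitivity estimate for Cohorts 2 and 3 falls mid-window for the second scan, so progression found at a late in-window scan counts as progression-free

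*SAP*

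**What the plan says.** The main benefit endpoint for Cohorts 2 and 3 counts patients shown by scan to be without progression at the second planned assessment or afterwards. Sixteen weeks appears only as an approximate label for that scan, and patients without a qualifying scan count as failures (SAP 2.7.1 and 3.2; Protocol 10.5.1 and 10.8.2).

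The supporting analysis is worded by time. SAP 2.7.1 says "Sensitivity analysis will be done by estimating PFS >16 weeks using K-M estimate", and SAP 3.2 says "Sensitivity analysis will be conducted using the K-M method to estimate PFS >16 weeks". Both protocol sections match.

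The other relevant rules are these:

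- PFS runs to "the date of the event defined as the first documented progression or death due to any cause, whichever is earlier" (SAP 2.7.1). Protocol Appendix 3 (14.3.6) has the actual scan date recorded.
- Protocol 7.1.3: "a treatment cycle will consist of 28 days".
- Protocol Table 7 puts tumour response at Cycle 3 Day 1 and then "Day 1 of every odd cycle".
- Protocol 7.1: for post-baseline imaging a ±7-day "window is allowed, except for the first post baseline assessment", which gets +7 days only. Protocol 7.2.1 gives ±7 days for the first scan as well. Both give ±7 days for the second.
- SAP 2.1.1.3 counts study day for safety as the event date minus "the start of study treatment plus 1", and SAP 2.5.1.2 also adds one day for exposure. No day-count rule is given for PFS.
- SAP 1: "The specifications for derived variable and datasets can be found in the" ADaM Reviewer's Guide, which is not among the documents.

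**The concern.** A sensitivity analysis should show whether the main result survives a different treatment of missing scans. Here the two analyses also differ in how they treat patients with nothing missing. A patient scanned within the window, but a few days late, and found to have progressed is a failure in one and a success in the other. No protocol deviation is needed for this.

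The discrepancy has one direction. With complete follow-up, a late second scan can move a patient only from failure to progression-free, never the reverse. If the Kaplan-Meier figure agrees with the scan-based rate or looks better, part of that may be a calendar effect. SAP section 1 says the plan may also serve outputs outside the study report, such as abstracts and manuscripts, so the figure may be read without this context.

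**Working it through.** **The plan's own figures.** The documents give no number for the Kaplan-Meier estimate. The scan-based figures beside it reproduce:

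- Cohort 3 continuation at a true rate of 20%: P(X ≥ 4 of 10) = 1 − (0.1074 + 0.2684 + 0.3020 + 0.2013) = 0.1209, consistent with the stated <12.1%.
- Largest exact 95% half-width for n = 20: 0.228, below the stated 23%.

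**Step 1: where the cut falls.**

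- Second scan = Cycle 5 Day 1 = 4 × 28 = 112 days after start.
- Its window is 112 ± 7 = 105 to 119 days, which is 15 days.
- 16 weeks = 16 × 7 = 112 days, the middle of that window.
- Third scan = 6 × 28 = 168 days; its window opens at 168 − 7 = 161 days.

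**Step 2: which scans are misclassified.** By plain date difference, PFS exceeds 112 days for scans on days 113 to 119, which is 7 of 15 days. If PFS is date difference + 1, a scan exactly on schedule gives PFS = 113, so days 112 to 119 are affected, 8 of 15.

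**Step 3: formula.** With complete follow-up and no deaths,

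K-M(112) − scan-based rate = P(first progression is found at scan 2 and that scan is dated after the cut).

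**Step 4: size under stated assumptions.** Scan dates are not in the documents, so this step is illustrative. Assume S(t) = exp(−λt), second scans even over 105 to 119 days, and first scans even over their window (56 to 63 days for +7; 49 to 63 for ±7). With s1 the mean of S at scan 1, the excess by plain difference is (7/15) × [s1 − mean S(113 to 119)].

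| Scan-based rate | First-scan window | λ | s1 | mean S(113–119) | Excess |
|---|---|---|---|---|---|
| 20% | +7 | 0.01439 | 0.4251 | 0.1885 | 11.0 points |
| 20% | ±7 | 0.01439 | 0.4476 | 0.1885 | 12.1 points |
| 40% | +7 | 0.00819 | 0.6145 | 0.3869 | 10.6 points |
| 40% | ±7 | 0.00819 | 0.6327 | 0.3869 | 11.5 points |
| 64.2% (median 175 days) | +7 | ln 2/175 = 0.00396 | 0.7901 | 0.6316 | 7.4 points |
| 64.2% (median 175 days) | ±7 | 0.00396 | 0.8012 | 0.6316 | 7.9 points |

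The 175-day median is the Cohort 1 figure in the Amendment 2 rationale, a different population. In a cohort of 20, 7.4 to 12.1 points is 1.5 to 2.4 patients.

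Other scan patterns, plain difference:

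- No second scan after day 112: excess 0.
- Half on the scheduled day and the rest even: 5.7 to 6.5 points for rates of 20% to 40%, and 4.0 to 4.2 at the 175-day median.

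**Step 5: a second model.** Take equal progression risk in each scan interval, s = √(rate), and a share f of second scans after the cut. Then K-M(112) = s × [1 − (1 − s)(1 − f)]. At a rate of 20%, s = 0.447, and f = 7/15 gives 0.447 × (1 − 0.553 × 0.533) = 0.315, an excess of 11.5 points.

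**Step 6: deaths, and the later cut.** With deaths as 3 of 39 PFS events (Amendment 2 rationale) in a simulation of 3,000,000 patients, the even-spread excess at 112 days is 9.8 to 11.2 points (6.8 to 7.3 at the 175-day median). At 126 days the scan-timing excess is 0, and deaths after scan 2 leave about −0.3 points.

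**The case against.** The strongest reply is that PFS >16 weeks is shorthand for having passed the second scan. The SAP's summary of changes for V1.0 speaks of introducing a definition under that name, the only definition in the text is scan-based, and no section prints 112 days. That may be what was meant. But a Kaplan-Meier estimate needs a time point, and the only one offered is 16 weeks. If shorthand was intended, a day number makes the text say so.

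A visit-mapping or day-count rule may also sit in the ADaM Reviewer's Guide. This cannot be excluded. The protocol and SAP contain no such rule.

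The size is mostly assumption. This stands. Scans are scheduled for a fixed day, the window is only a tolerance, and nothing in the documents supports an even spread.

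The two figures are expected to differ anyway: Kaplan-Meier censors patients lost without an event, and a patient who misses only scan 2 and progresses at scan 3 is still progression-free at the cut. Those differences are what the sensitivity analysis is for. The scan-timing effect is not.

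A reader might infer a bias of more than 20 points. That needs every second scan to be late (22.5 to 26.1 points for rates of 20% to 40%), or a + 1 rule with every scan on schedule (21.5 to 24.8). The documents support neither: scan dates are unknown, and the + 1 rule is stated for safety study day and exposure, not for PFS.

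**Conclusion.** The mismatch is real on the text, but minor. Read at 16 weeks, the sensitivity estimate counts progression found at in-window second scans on days 113 to 119 as progression-free, while the main rate counts it as failure. If PFS is counted with + 1, progression at an on-time scan is also counted as progression-free. With complete follow-up the effect can only raise the Kaplan-Meier figure. Its size runs from 0 (no second scan after day 112, plain difference) to about 7 to 12 points under an even spread, which is an assumption together with exponential PFS.

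A reader might go further and infer that the benefit conclusion or the expansion of Cohort 3 is inflated. The documents do not support that. The binomial rate, the requirement that its lower bound exclude 20%, and the rule of at least 4 of 10 all use the scan-based count. Both cohorts are exploratory, and no decision rule uses the Kaplan-Meier figure. The change is optional.

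**What to change.** In SAP 2.7.1 and 3.2, read the Kaplan-Meier estimate after the second-scan window closes and before the third opens, that is, after 119 and before 161 days from start; 126 days (18 weeks) is one choice. Label the output with that time point. State whether PFS is a date difference or a date difference + 1; 126 days works under either, since an in-window second scan gives at most 119 or 120 days. Record the change in SAP section 4, which now declares none, and align Protocol 10.5.1 and 10.8.2 at the next amendment.

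The cost is a short text edit, with no new data and no effect on patients. There are two small downsides: the figure is no longer a nominal 16-week rate, and the few deaths between the second scan and day 126 count as events. The edit removes the effect for in-window scans only.
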